**Table 1 - AESI and search criteria**

AESI flag	Searcha criteria
Leukopenia	SMQ: Haematopoietic leukopenia
Thrombocytopenia	SMQ: Haematopoietic thrombocytopenia
Infections (Opportunistic infections, Tuberculosis)	Primary SOC: Infections and infestations (CRF checkbox: Opportunistic infections; HLT Tuberculosis infections)
Hepatic disorders	SMQ : Drug-related hepatic disorders – comprehensive search
Diverticulitis/potential GI perforations b	SMQ: Gastrointestinal perforation and HLT: Diverticulum inflammations
GI ulcerations	SMQ: Gastrointestinal ulceration
Elevation in lipids	SMQ: Dyslipidemias
Anaphylaxis	SMQ: Anaphylactic reaction
Hypersensitivity	SMQ Hypersensitivity
Injection site reactions	HLT Injection site reactions
Malignancy	SMQ: Malignant or unspecified tumours Excluding non-melanoma skin cancer: SMQ Malignant or unspecified tumours excluding HLT of Skin neoplasms malignant and unspecified (excl melanoma)
Lupus-like syndrome	SMQ: Systemic lupus erythematosus
Demyelinating disorders	SMQ: Demyelination
Pregnancy c	CRF checkbox: Pregnancy
Overdose c	CRF checkbox: Symptomatic overdose

a All SMQs are narrow search  b These events will be further reviewed to identify cases of GI perforations  c Standard AESI applies to all Sanofi studies
	

### ***Cardiovascular Adjudication Committee***

All deaths and potential CV events reported by the investigator, identified by pre-specified search criteria described in the Cardiovascular Adjudication Committee (CAC) charter will be prospectively adjudicated in a blinded manner by the CAC. The committee will adjudicate qualifying events according to the CAC Charter.

The CV adjudication committee will adjudicate each event as: a CV event, a non-CV event or not evaluable ([Appendix J](#) provides further categorization of CV event, non-CV event).

Two composite Major Adverse Cardiac Events (MACE) endpoints are defined as:

- MACE (primary): CV Death, MI, Stroke, Hospitalization for unstable angina (UA) or Hospitalization for Transient Ischemic Attack (TIA).
- MACE (narrow): CV Death, MI, or Stroke.

#### **2.1.3.2 Deaths**

The deaths observation period are per the observation periods defined above:

- Death on-treatment: deaths occurring during the treatment period
- Death during follow-up: deaths occurring during the follow-up period
- Death post-study: deaths occurring during the post-study period

#### **2.1.3.3 Laboratory safety variables**

Clinical laboratory data consists of blood analysis, including hematology, clinical chemistry and urinalysis. Clinical laboratory values will be converted to standard international units; international units will be used in all listings and tables. In addition, the lipids parameters will also be summarized in US units.

Blood samples for clinical laboratories will be taken at Visits 1-49 and/or early termination unless otherwise specified. The laboratory parameters will be classified as follows:

- Hematology
  - **Red blood cells and platelets and coagulation:** hemoglobin, hematocrit, platelet count, RBC, RBC morphology (if RBC count is abnormal), and prothrombin time.
  - **White blood cells:** WBC, WBC differential (neutrophils/ANC, lymphocytes, monocytes, basophils, eosinophils)

- Clinical chemistry
  - **Metabolism:** total cholesterol, HDL, LDL, ratio of HDL versus LDL (HDL:LDL), triglycerides tests; glucose and total protein in fasting condition; HbA1c; Apolipoprotein A and B (determination is not performed in SFY13370 and results will not be available for the initial LTS11210 visit for SFY13370 patients); and acute phase reactants: hs-CRP.
  - **Electrolytes:** sodium, potassium, chloride, calcium, and bicarbonate.
  - **Renal function:** creatinine, CLcr, BUN, uric acid.
  - **Liver function:** ALT/SGPT, AST/SGOT, ALP, albumin, total bilirubin, conjugated and unconjugated bilirubin, and LDH.
  - **Antibody:** anti-CCP antibodies, RF, ANA/anti-ds DNA.
  - **Pregnancy test :** Serum  $\beta$ -hCG for all female patients.

Urine samples will be collected as follows (when urine dipstick is abnormal at site):

- **Urinalysis** - quantitative analyses: pH, specific gravity, ketone, proteins, blood, glucose, bilirubin, urobilinogen, nitrate and leukocytes.

Technical formulas are described in [Section 2.5.1](#).

#### **2.1.3.4 Vital signs variables**

Vital Signs include: Heart Rate (HR), Systolic and Diastolic Blood Pressure (SBP and DBP) according to position (standing and supine), as well as orthostatic changes in blood pressure (standing – supine). It also includes weight and temperature.

#### **2.1.3.5 Electrocardiogram variables**

A standard 12-lead ECG will be performed and will be determined using centralized automatic and manual readings.

ECG parameters include Heart Rate, PR, QRS, QT as well as corrected QTc (according to Bazett/Fridericia), ST deviation, T-wave morphology, and U wave presence or absence.

#### **2.1.4 Efficacy endpoints**

Efficacy is a secondary endpoint of this study. The efficacy variables will include:

- ACR20 response over time up to Week 264
- ACR50 and ACR70 response over time up to Week 264
- Change from baseline in ACR components up to Week 264
- DAS28 –CRP response over time

- DAS28 remission over time
- EULAR response over time
- Change from baseline in the van der Heijde modified total Sharp score (for patients from EFC11072 Part B Cohort 2 and Cohort 1 selected dose arms with an end of treatment X-ray evaluation) at Weeks 48, 96, 144 and 192 or EOT if EOT is prior to Week 192
- Incidence of radiographic progression of the van der Heijde modified total sharp score at Weeks 48, 96, 144, and 192 or EOT if EOT is prior to Week 192
- Change from baseline in HAQ-DI over time up to Week 264.

Note that TJC and SJC (both based on 28 joints), patient's global assessment of disease activity and hs-CRP will still be assessed after Week 264 to calculate DAS28.

As mentioned before, the baseline value for efficacy parameters is the original baseline from the previous study databases for patients who rolled over to LTS11210.

#### **A) ACR20 response over time**

To be classified as an ACR20 Responder, a patient must achieve 20% improvement in the Tender joint count (68 joints) and the Swollen joint count (66 joints), as well as 20% improvement in at least 3 of the following 5 assessments:

- Levels of an acute phase reactant (CRP level)
- Patient's assessment of pain based on the 0 – 100mm Visual Analogue Scale (VAS)
- Patient's global assessment of disease activity based on the VAS
- Physician's global assessment of disease activity based on the VAS
- Patient's assessment of physical function based on the HAQ\_DI

The 7 ACR components assessing the signs and symptoms of RA are measured as follows

##### a) Tender Joint Count (TJC)

A total of 68 joints will be assessed for tenderness. The 68 joints to be examined for tenderness are: temporomandibular (n=2), sternoclavicular (n=2), acromioclavicular (n=2), shoulder (n=2), elbow (n=2), wrist (n=2), metacarpophalangeal (n=10), interphalangeal of thumb (n=2), distal interphalangeal (n=8), proximal interphalangeal (n=8), hip (n=2), knee (n=2), ankle mortise (n=2), ankle tarsus (n=2), metatarsophalangeal (n=10), interphalangeal of great toe (n=2), and proximal/distal interphalangeal of the toes (n=8).

A formal count of the joints will be performed by a trained independent assessor. Joint tenderness is defined as pain induced by the pressure of the joints, exerted by the assessor's thumb and index finger. The assessor will classify each joint as painful yes/no and swollen yes/no. A score of 0/1 will be given to each tender joint with 0 representing no pain and 1 representing pain. The tender joint count ranges from 0 to 68 where 0 is considered the best and 68 the worst.

b) Swollen Joint Count (SJC)

The 66 joints to be examined for swelling are the same as those examined for tenderness, except the hip joints are not included.

A formal count of the joints will be performed by a trained independent assessor. The assessor will classify each joint as swollen yes/no. A score of 0/1 will be given to each swollen joint with 0 representing no swollen and 1 representing a swollen joint. The swollen joint count ranges from 0 to 66 where 0 is considered the best and 66 the worst.

c) Physician's Global Assessments of Disease Activity

Physician's global assessments of the patient's current disease activity will be assessed on an anchored 100 mm horizontal VAS where 0 is considered the best disease activity (no disease activity) and 100 the worst (most disease activity).

d) Patient's Global Assessments of Disease Activity

Patient's global assessments of their current disease activity will be rated on an anchored 100 mm horizontal VAS where 0 is considered the best disease activity (no disease activity) and 100 the worst (most disease activity).

e) Patient's Assessment of Pain

Patients will be requested to indicate their pain intensity due to their RA using a 100 mm horizontal VAS where 0 is considered "No pain" and 100 "the worst pain you can imagine".

f) Patient's Assessment of Physical function – Health Assessment Questionnaire Disease Index (HAQ-DI)

The HAQ-DI is a standardized questionnaire developed for use in RA. The HAQ-DI, with the past week as the time frame, focuses on whether the respondent "is able to..." do the activity and covers 8 categories in 20 items: dressing and grooming, arising, eating, walking, hygiene, reach, grip and activities, for which there are at least 2 questions by category. The 4 responses for the HAQ-DI questions are graded as follows: without any difficulty = 0; with some difficulty = 1; with much difficulty = 2; and unable to do = 3. To calculate the Standard HAQ-DI Score (With Aids/Devices), there are 3 steps

1. Sum the 8 category scores by using the highest sub-category score from each category.
  - For example, in the category ARISING there are 3 sub-category items. A patient who responds with a 1, 2, and 0, respectively, results in category score of 2.
2. Adjust for use of aids/devices and/or help from another person when indicated.
  - Adjust the score for a category by increasing a 0 or a 1 to a 2.
  - If a patient's highest score for that sub-category is a 2 it remains a 2, and if a 2, it remains a 2.
  - The data entered at field "Other specify" will not be used for score adjustment.

3. Divide the summed category scores by the number of categories answered (must be a minimum of 6) to obtain a HAQ-DI score of 0-3 (3=worst functioning).

A HAQ-DI score cannot be calculated validly when there are scores for less than 6 of the 8 categories. HAQ-DI scoring ranges between 0 and 3. A high HAQ-DI score has been found to be a strong predictor of morbidity and mortality in RA.

g) The level of an acute phase reactant measured by CRP

High sensitivity CRP will be assessed centrally. Since CRP levels are directly correlated with Interleukin 6 receptor (IL6-R) activity, it is expected that active dose regimens will have a dramatic lowering effect on CRP levels.

The ACR components are further described in

**Table 2 - ACR components**

ACR component	Range	Direction
TJC	0-68	Lower is better
SJC	0-66	Lower is better
Pain VAS	0-100	Lower is better
Patient global VAS	0-100	Lower is better
Physician global VAS	0-100	Lower is better
HAQ-DI	0-3	Lower is better
CRP ( mg/dL)	>0	Lower is better

TJC: Total Joint Counts, SJC: Swollen Joint Counts, VAS: Visual Analog Scale

**B) ACR50 response over time**

ACR50 is defined as the percentage of patients who achieve at least 50% improvement in both tender joint count and swollen joint count, and at least 50% improvement in at least 3 of the 5 remaining ACR components.

**C) ACR70 response over time**

ACR70 is defined as the percentage of patients who achieve at least 70% improvement in both tender joint count and swollen joint count, and at least 70% improvement in at least 3 of the 5 remaining ACR components.

**D) Change in ACR components over time**

The change in each ACR component will be calculated from baseline of the previous studies.

**E) DAS28-CRP over time**

DAS28-CRP is a composite score that includes 4 variables:

- Tender joints count (based on 28 joints: shoulder (n=2), elbow (n=2), wrist (n=2), metacarpophalangeal (n=10), interphalangeal of thumb (n=2), proximal interphalangeal (n=8), knee (n=2))
- Swollen joints count (based on 28 joints: shoulder (n=2), elbow (n=2), wrist (n=2), metacarpophalangeal (n=10), interphalangeal of thumb (n=2), proximal interphalangeal (n=8), knee (n=2))
- General health (GH) or patient's global assessment of disease activity based on VAS (mm) assessed from the ACR questionnaire
- Marker of inflammation here assessed by the hs-CRP ( mg/L).

It is a continuous measure allowing for measurement of absolute change in disease burden and percentage improvement. It has been extensively validated for its use in clinical trials and accepted by health authorities. Using this data, the DAS28 can be calculated using the following formula:

$$\text{DAS28-CRP} = 0.56 \times \sqrt{28\text{TJC}} + 0.28 \times \sqrt{28\text{SJC}} + 0.36 \times \text{Log}(\text{CRP}+1) + 0.014 \times \text{GH} + 0.96,$$

Where 28TJC and 28SJC are the tender and swollen joint counts from 28 joints and GH is the patient's global assessment of disease activity and CRP is in mg/L.

DAS28-CRP provides a number on a scale from 0 to 10 indicating the current activity of the RA.

DAS28 –CRP will be considered as missing if one of the components is missing.

#### **F) DAS28 remission over time**

DAS28 Remission is the event of having a DAS28-CRP score <2.6.

#### **G) European League Against Rheumatism (EULAR) response over time**

The European League Against Rheumatism (EULAR) response criteria combine the DAS28 score at the time of evaluation with the change in DAS28 score between 2 time points. The EULAR response criteria are defined as:

- Good response = The event of having an improvement of >1.2 and a present DAS28-CRP score  $\leq 3.2$ .
- Moderate response = The event of having either an improvement of >0.6 to  $\leq 1.2$  and a present DAS28-CRP score  $\leq 5.1$ , OR, having an improvement of >1.2 and a present DAS28-CRP score >3.2.
- No response = The event of having either an improvement of  $\leq 0.6$ , OR, having an improvement of >0.6 to  $\leq 1.2$  and a present DAS28-CRP score >5.1.

**Table 3 - EULAR response categories**

DAS28-CRP score	Change from baseline in DAS28-CRP score		
	< -1.2	< -0.6 to $\geq$ -1.2	$\geq$ -0.6
$\leq$ 3.2	Good response	Moderate response	No response
> 3.2 to $\leq$ 5.1	Moderate response	Moderate response	No response
> 5.1	Moderate response	No response	No response

## H) Change in van der Heijde modified total Sharp score over time

X-ray data will be collected for patients from EFC11072 Part B Cohort 2 and Cohort 1 selected dose arms only. The degree of joint damage will be assessed using the van der Heijde modified total Sharp score (mTSS). This methodology quantifies the extent of bone erosions for 44 joints and joint space narrowing for 42 joints, with higher scores representing greater damage. The van der Heijde mTSS at a time point is the sum of the scores from both the erosion score and the joint space narrowing score, for a maximum score of 448.

### *Erosion score*

The joint erosion score is a summary of erosion severity in 32 joints of the hands and 12 joints of the feet. Each joint is scored, according to the surface area involved, from 0 to 5 for hand joints and 0 to 10 for the joints of the foot. The maximum erosion score (5 for the hand and 10 for the foot) indicates extensive loss of bone from more than one half of the articulating bone. A score of 0 in either the hand or foot indicates no erosion. The maximum erosion score is 280 (160 in the hands and 120 in the feet) for a time point.

### *Joint space narrowing score*

The joint space narrowing (JSN) score summarizes the severity of JSN in 30 joints of the hands and 12 joints of the feet. Assessment of JSN for each hand (15 joints per hand) and foot (6 joints per foot), including subluxation, is scored from 0 to 4, with 0 indicating no/normal JSN and 4 indicating complete loss of joint space, bony ankylosis or luxation. Thus, the maximum JSN score is 168 at a time point.

### *X-ray data reading*

#### Campaign 1

X-rays read in Campaign 1 will include baseline and EOT (or last available visit) from EFC11072, Week 48 and any unscheduled visits between Week 0 and Week 48 in LTS11210. Two primary readers and an adjudicator will perform reading of data up to Week 48 in LTS11210 (see details in [Appendix D](#)). The X-rays at baseline and Year 1 (EOT or last available visit in EFC11072) will be reread.

The linear extrapolation method will be used to impute missing modified total Sharp score, erosion score, or joint space narrowing score at Week 48 in LTS11210 from Campaign 1 data for patients who have EOT (or last available data) in EFC11072 and any unscheduled visit data between Week 0 and Week 48 in LTS11210. In the linear extrapolation method, for example, the missing modified total Sharp score at Week 48 is imputed according to the following formula:

$$\text{Week 48 modified total Sharp score} = \text{EOT score in EFC11072} + 336 * (\text{modified total Sharp score of the last measurement in LTS11210} - \text{EOT score in EFC11072}) / (\text{date of last measurement in LTS11210} - \text{date of EOT visit in EFC11072}).$$

### Campaign 2

X-rays in Campaign 2 will include baseline from EFC11072, Weeks 48 and 96, and any unscheduled visits between Week 48 and Week 96 in LTS11210. The linear extrapolation method will be used to impute missing the modified total Sharp score, erosion score, or joint space narrowing score at Week 96. Similarly, the missing modified total Sharp scores at Week 96 are imputed by the linear extrapolation method according to the following formula:

$$\text{Week 96 modified total Sharp score} = \text{Week 48 score} + 336 * (\text{modified total Sharp score of the last measurement} - \text{Week 48 score}) / (\text{date of last measurement} - \text{date of Week 48 measurement}),$$

### Campaign 3

X-rays in Campaign 3 will include baseline from EFC11072, Weeks 96, 144 and 192 (or EOT), and any unscheduled visits between Week 96 and Week 192 (or EOT) in LTS11210. The linear extrapolation method will be used to impute missing the modified total Sharp score, erosion score, or joint space narrowing score at Weeks 144 and 192 in LTS11210 based on Campaign 3 data. Similarly, the missing modified total Sharp scores at Week 144 and Week 192 in LTS11210 are imputed by the linear extrapolation method according to the following formula:

$$\text{Week 144 modified total Sharp score} = \text{Week 96 score} + 336 * (\text{modified total Sharp score of the last measurement} - \text{Week 96 score}) / (\text{date of last measurement} - \text{date of Week 96 measurement}),$$

$$\text{Week 192 modified total Sharp score} = \text{Week 96 score} + 672 * (\text{modified total Sharp score of the last measurement} - \text{Week 96 score}) / (\text{date of last measurement} - \text{date of Week 96 measurement}),$$

Where EOT visit for X-ray in LTS11210 will be prior to Week 192 if a patient discontinues the study prior to Week 192.

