The duration of the treatment period in the study will be at least 264 weeks, or up to a maximum of 516 weeks (*except in the UK where the duration of treatment will be 264 weeks*) described in Protocol Amendment 9. However, some patients may complete this study with 260 week treatment duration per Protocol Amendment 8 before the approval of Protocol Amendment 9 in their countries. The total maximum duration of study participation for a patient may be up to 523 weeks.

- 1-week screening period if applicable
- 516-week maximum treatment period in LTS11210 (for the earliest patients enrolled in LTS11210 in 2010 if sarilumab is not commercialized by 2020)
- 6-week follow up period as required per protocol

Patients will either enter a 1-week screening period after the EOT visit (Visit 1 in LTS11210) in initial studies (for patients from EFC11072 Part A or Part B1 and ACT11575), or enrol directly into the treatment period (for patients from EFC11072 Part B2, EFC10832, SFY13370, or EFC13752, the EOT visit in the initial study corresponds to the randomization visit, Visit 1/2 in LTS11210).

At Visit 2 or Visit 1/2 (Week 0) after confirmation of eligibility, patients will be administered the first open-label dose of sarilumab at the investigational site and will be observed for 30 minutes for any medical events. At dosing time points occurring outside site visits, sarilumab can be injected by the patients, or by trained caregivers.

Patients will return for the safety follow-up visit 6 weeks after the EOT visit (V49). In case of early treatment discontinuation, patients are required to complete the EOT visit (V49) and to return for the 6-week safety follow-up visit (Visit 50) as well.

The study will be considered completed for a patient at the time he/she completes all the scheduled procedures.

An optional 12-week sub-study aiming to evaluate the usability of pre-filled syringe with safety system (PFS-S) will be conducted in some countries. Patients enrolled in LTS11210 at selected sites in those countries may participate in the PFS-S sub-study from Week 24 of the main study after providing written informed consent for the sub-study. However, patients may continue to participate in the main trial without participating in the PFS-S sub-study if they wish. Full details of the PFS-S sub-study are presented in [Appendix K](#).

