#### **2.4.5 Analyses of efficacy endpoints**

There will be no confirmatory analysis for the efficacy variables. All analysis will be done descriptively on the safety population by visit in observed case, as appropriate. In addition to the by-visit analysis, efficacy assessments summarized on a yearly basis will be provided.

The baseline value for efficacy parameters is the original baseline from the previous studies. The value at Week 0 is the last non-missing measurement in data collected at scheduled visits: visit1, visit2, and/or visit1/2 in LTS11210 or EOT visit of previous studies prior to first IMP in LTS11210 study.

For categorical variables, for example, percentage of patients who have maintained/reached ACR20 overtime, the number and percentage will be provided from all patients who have data available at that time point, and the 95% confidence intervals (CI) will be calculated if appropriate.

For continuous variables, descriptive statistics such as the mean, standard deviation, median, minimum and maximum will be provided. In addition, 95% confidence interval of the mean will be presented. This applies to the original values and change (or percent change) from baseline.

The 2-year (EFC11072 52 weeks + LTS11210 48 weeks) X-ray data from Campaign 1 will be described using the van der Heijde modified total Sharp score for the subset of patients who previously completed study EFC11072, Part B when the 2-year X-ray data are available for all these patients. The modified total Sharp score and the change from baseline in the modified total sharp score will be described using mean, standard deviation, median, minimum and maximum, along with 95% confidence intervals. There is no formal treatment comparison and no alpha adjustment will be made (further analyses will be in the report of integrated summary of efficacy). In addition, the incidence of radiographic progression will be summarized using descriptive statistics.

The above analyses will also be performed for X-ray data from Campaign 2 and Campaign 3 respectively once X-ray data are available.

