## **2.5.4 Windows for time points**

For efficacy parameters (except X-ray), a discontinuation visit (EOT, Visit 49) will be mapped to the scheduled visit for the analyses. If a discontinuation visit happens at a regular visit, then the visit number will be reassigned as the regular visit number where an assessment is planned. If a discontinuation visit happens between 2 regular visits, then the visit number will be reassigned to the next visit number where an assessment is planned. For example, if a discontinuation visit happens between Visits 9 and 10, then the visit number will be reassigned as 10. Similarly, the EOT visit (Visit 49) for patients who complete the study with 260-week treatment duration per Protocol Amendment 8, will be mapped to the Visit 28.

For X-ray data, the linear extrapolation method for the modified total Sharp score, the erosion score, and the joint space narrowing score will use true date to extrapolate missing values at Weeks 48, 96, 144, and 192 with no visit remapping.

All efficacy analyses will be performed by the nominal visit number and no visit window will be defined.

For safety assessments, the reference date for the derivation of relative days of events or findings will be the date of first drug intake as documented in the study drug administration page of the eCRF. Selected safety variables will be summarized using the visit window defined in [Table 6](#) for the by-visit descriptive analysis. Note that only the laboratory measurements performed at the central laboratory will be used for the by-visit descriptive analysis. All available values obtained between two visits including unscheduled measurements will be assigned to the appropriate visit window. The following rule will be applied when mapping the measurements to the visit:

1. When a patient has more than one measurement on the same laboratory parameter (or vital sign or ECG) on the same date, then the one with the later/largest sample ID will be used.
2. For the same laboratory parameter (vital sign or ECG), if a patient has more than one measurement at different dates within the same visit window, the scheduled measurement that is closest to the target date will be used. If there is no scheduled measurement within the visit window, the unscheduled measurement that is closest to the target date will be used.

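### SAP 2.1.4 H, Campaign 1: the fixed 336-day step reaches LTS11210 Week 48 from an EFC11072 EOT film, but not from the earlier last-available film that the same paragraph allows as anchor

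*SAP*

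**What the plan says.** The rule is in SAP 2.1.4 H, under X-ray data reading. On the film set it says: "X-rays read in Campaign 1 will include baseline and EOT (or last available visit) from EFC11072". The LTS11210 Week 48 film and any unscheduled LTS11210 films up to Week 48 are added. A missing Week 48 score (total, erosion or joint space narrowing) is imputed by linear extrapolation "for patients who have EOT (or last available data) in EFC11072 and any unscheduled visit data between Week 0 and Week 48 in LTS11210".

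One formula is printed. In symbols, the imputed Week 48 score is the EFC11072 EOT score, plus 336 times (last LTS11210 score minus EOT score), divided by (date of the last LTS11210 measurement minus the "date of EOT visit in EFC11072"). There is no second version for a patient whose EFC11072 film is the last available one rather than the EOT film.

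SAP 2.5.4 adds that the X-ray extrapolation "will use true date to extrapolate missing values at Weeks 48, 96, 144, and 192 with no visit remapping". SAP 2.4.5 describes the product as "The 2-year (EFC11072 52 weeks + LTS11210 48 weeks) X-ray data from Campaign 1".

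On timing, SAP 1.1 says that for Part B Cohort 2 "the EOT visit in the initial study corresponds to the randomization visit, Visit 1/2 in LTS11210". For Part B Cohort 1 it says: "Patients will either enter a 1-week screening period after the EOT visit (Visit 1 in LTS11210) in initial studies". Protocol 12.1.9 restricts LTS11210 films to patients who completed EFC11072 Part B (Cohort 2 and the selected-dose arms of Cohort 1), with a window of ±14 days.

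**The concern.** The paragraph admits two kinds of anchor film, but its formula fits only one. A step of 336 days lands on LTS11210 Week 48 only if it starts at LTS11210 Day 1. An EOT film is at or next to Day 1. A last-available film is earlier by an amount that the formula never uses.

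The two SAP sections also point to different dates for such a patient. The printed formula names the EOT visit date, while SAP 2.5.4 calls for true dates. Two programmers could each follow the SAP and obtain errors of opposite sign.

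The imputed scores feed the mean change from baseline in the 2-year X-ray summary. They can also feed the progression rate, because any change from baseline above 0 counts as progression (Protocol 13.5.5; SAP 2.1.4 I).

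**Working it through.** **Inputs**
- Step in the Campaign 1 formula: 336 days (SAP 2.1.4 H).
- LTS11210 Week 48: target Day 337 (SAP Table 6, used here only as a day count).
- Gap from the EFC11072 EOT visit to LTS11210 Day 1: 0 days for Part B Cohort 2, and 1 to 7 days for Cohort 1 (SAP 1.1 and 1.4.3.1).
- g: days from the anchor film to LTS11210 Day 1. The EFC11072 film schedule is not in the documents, so a range is assumed.
- d: days from LTS11210 Day 1 to the unscheduled LTS11210 film (assumed).
- r: a constant progression rate, assumed to be 1 unit per year, that is 1/365.25 per day.

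**The plan's own figure.** 48 × 7 = 336, and 337 - 1 = 336. The figure is reproduced, for an anchor dated at Day 1.

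**EOT film as anchor.** For Cohort 2, g = 0 and the formula reaches Week 48 exactly. For Cohort 1 with g = 7, it reaches day 336 - 7 = 329, which is Week 47.0. At 1 unit per year that is an error of -7/365.25 = -0.02 units.

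**Last-available film as anchor.** Take a score that rises in a straight line at rate r.

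*Film's own date in the denominator.* The slope is correct, but the step starts g days early. The value obtained belongs to LTS day 336 - g, and the error is -r × g.

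*EOT visit date in the denominator, taken as Day 1.* The score difference built up over d + g days is divided by d days. The slope is inflated by (d + g)/d, and the error is r × g × (336/d - 1).

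| g (days) | Film date: LTS week reached | Film date: error | EOT date, d = 168: slope factor | EOT date, d = 168: error |
|---|---|---|---|---|
| 28 | 44 | -0.08 | 1.17 | +0.08 |
| 84 | 36 | -0.23 | 1.50 | +0.23 |
| 196 | 20 | -0.54 | 2.17 | +0.54 |
| 252 | 12 | -0.69 | 2.50 | +0.69 |

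The EOT-date error depends on d and shrinks towards 0 as d approaches 336.

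**One patient (assumed values).** The anchor film is 196 days before Day 1 with score 10, and the LTS11210 film is at day 168 with score 13.
- Film date: 10 + 336 × 3/364 = 12.77.
- EOT visit date: 10 + 336 × 3/168 = 16.00.
- Correct horizon of 336 + 196 = 532 days: 10 + 532 × 3/364 = 14.38.

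The film-date result is for day 140 (Week 20), before the patient's own Week 24 film. This happens whenever 336 - g is less than d.

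**Check of the correction.** With 336 + g as multiplier and the film's own date in the denominator, the error on a straight line is 0 for every g and d tried. With g = 0 the expression is the printed formula.

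**Campaigns 2 and 3.** Their anchors are LTS11210 Week 48 and Week 96 films. The steps of 336 and 672 (96 × 7) match those anchors, apart from the ±14-day film window.

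**The case against.** The strongest reply is that the printed formula is correct for the anchor that it names, and that the fallback hardly ever arises. Much of this stands.

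- LTS11210 films are taken only in Part B completers, and the EFC11072 EOT film is among the entry items in Protocol 12.1.1 and 12.1.2.2. An affected patient must have finished Part B without an EOT film, have no LTS11210 Week 48 film, and have an earlier unscheduled LTS11210 film.
- The endpoint list in SAP 2.1.4 (and Protocol 13.2.3) confines the mTSS change to patients with an end-of-treatment X-ray. If that means the EFC11072 EOT film, the fallback patients drop out of the mean-change analysis. The text does not say which study's EOT is meant. If they do drop out, the fallback wording in 2.1.4 H serves no purpose in that analysis.
- SAP 2.5.4 makes the film-date reading the likelier one. It settles the denominator, but it leaves the 336 fixed, so Week 48 is still missed.

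A reader might infer three stronger things that the documents do not support. The first is that 336 is wrong in general; it is right for EOT films, and the Cohort 1 gap lies well inside the ±14-day window. The second is that the large inflation of the EOT-date reading is the expected error; it rests on the less likely reading and on assumed values of g and d. The third is that the progression rate is distorted across the board. A patient's status changes only if the baseline score lies between the correct and the computed value, that is, where the fitted line crosses baseline in that stretch. No such case can be shown from the documents.

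**Conclusion.** The point holds for one subgroup: patients whose EFC11072 anchor is a last-available film before EOT. For them the stated rule does not give a Week 48 score under either reading. The film-date reading is too low for a worsening score by r × g, and the EOT-date reading is too high when d is below 336.

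At the assumed 1 unit per year, the film-date error runs from -0.08 units (g = 28 days) to -0.54 (g = 196 days), and it scales in proportion to the rate. These sizes rest on a straight-line course and on assumed gaps. The number of patients is not stated and is probably small.

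The effect is confined to the 2-year mTSS summary, which is descriptive and carries no formal treatment comparison (SAP 2.4.5), and to occasional progression calls. This is a minor correction to a prespecified imputation rule.

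**What to change.** Replace the Campaign 1 formula in SAP 2.1.4 H by: anchor score + (LTS11210 first-dose date + 336 - anchor film date) × (last LTS11210 score - anchor score) / (date of last LTS11210 film - anchor film date). Define the anchor film as the EFC11072 EOT film or, if there is none, the last available EFC11072 film, with its own date. The dates needed are those of the films and of the first LTS11210 dose, so no new data are required. Results for anchors at Day 1 do not change.

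The alternative is to delete the last-available fallback and impute only for patients with an EFC11072 EOT film. That would agree with the end-of-treatment X-ray restriction in SAP 2.1.4 if the restriction refers to EFC11072, which should then be stated. It has a side effect: SAP Appendix C counts a missing change from baseline as progression, so fallback patients left without a Week 48 value would be counted as progressors if they stay in that analysis. The first option avoids this and costs one line.
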